## 5.0 STUDY PROCEDURES AND SCHEDULE OF ASSESSMENTS

### 5.1 Patient Identification

Eligible patients will be referred by members of the MD Anderson Department of Breast Medical Oncology or screened through electronic medical records and our Departmental database. Process for consent is detailed in Section 9.

### 5.2 Schedule of Assessments

Table 1 – Study Procedures and Assessments Phase I

	Baseline	C1 W1	C1 W2	C1 W3	C1 W4	C2 W5	C2 W6	C2 W7	C2 W8	C3 W1	C4+ W1	Off Study
Day		D1	D8	D15	D22	D1	D8	D15	D22	D1	D1	
Scheduling timeframe	-14d	+/- 2	+/- 2	+/- 2	+/- 2	+/- 2	+/- 2	+/- 2	+/- 2	+/- 2	+/- 2	Within 30 D
Laboratory	X A	X	X	X	X	X	X	X	X	X	X	X
Adverse event assessment)		X	X	X	X	X	X	X	X	X	X	X
Physical exam/ Weight/Vital signs	X A	X	X	X	X	X	X	X	X	X	X	X
ECOG performance status evaluation	X											
Ophthalmologic Exam	X B											X
Imaging Assessments	X A								X C			
Tumor Biopsy	X C					X C						
Palbociclib		X	X	X	X	X	X	X	X	X	X	
HCQ		X	X	X	X	X	X	X	X	X	X	
Letrozole		X	X	X	X	X	X	X	X	X	X	

Table 2 – Study Procedures and Assessments Phase II

	Baseline	W1	W2	W3	W4	W5	Off Study
Day		D1	D8	D15	D22	D29	
Scheduling Window	-14 D	+/- 2	+/- 2	+/- 2	+/- 2	+/- 2	Within 30 D
Laboratory	X A	X	X	X	X	X	X
Adverse event assessment)		X	X	X	X	X	X
Physical Exam/Weight/Vital Signs	X A	X	X	X	X	X	X
ECOG performance status evaluation	X	X	X	X	X	X	X
Ophthalmologic Exam	X B						X
Breast ultrasound	X A					X	
Research blood	X A			X		X	X
Biopsy (or surgery)	X A			X		X D	
Low dose palbociclib + letrozole		X	X	X	X		
HCQ				X	X		

Abbreviations: W=week (week 1 is the same as day 1 prior to starting palbociclib); HCQ = hydroxychloroquine; D = day; W = week

Laboratory assessments: Baseline, then weekly x 8 for Phase I and x 4 for Phase II, then as indicated until off study labs include CBC/differential, electrolytes, BUN, creatinine, glucose, albumin, AST, ALT, total bilirubin, alkaline phosphatase. Baseline only: PT, PTT, urinalysis with microscopic exam. Baseline urine or serum pregnancy test for both Phase I and II.

Superscripts:

A= Phase I: Laboratory assessment must be done within 14 days of C1 D1. Any imaging assessments already completed during the regular work-up of the patient within 28 days prior to starting study treatment, including before signing the main study ICF can be considered as the baseline images for this study; Phase II: done within 2 weeks prior to starting therapy (low dose palbociclib/letrozole).

B= done within 8 weeks prior to starting study medication

C= Phase I – baseline biopsy can of metastatic tumor pre-treatment or primary lesion (optional) or can be from archival tissue if available (either primary or metastasis). Week 5 biopsy (optional) can be +/- 1 week. Phase II – biopsies are mandatory- third biopsy done either at W5 for patients going on to surgery at that time, for those waiting until between weeks 20-24, biopsy done pre-operatively. Patients who know in advance that they will proceed with surgery at T2 will not need a biopsy and biomarkers will be measured on the surgical specimen. Imaging will be done at end of Cycle 2 (Week 8) +/- 1 week (prior to cycle 3 drug), and every 8-12 weeks (+/- 2 weeks) thereafter

D= Phase II – Sample of surgical specimen (or core needle biopsy if patients is going on to standard of care neoadjuvant endocrine or chemotherapy) will be taken for analysis as outlined in Section 5.3.

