## ABBREVIATIONS AND LIST OF DEFINITIONS OF TERMS

Abbreviation	Term/Definition
Akt	A growth factor pathway component (serine-threonine kinase)
Alk Phos	Alkaline phosphatase
ALT	Alanine aminotransferase
ANC	Absolute neutrophil count
AST	Aspartate aminotransferase
ASCO/CAP	American Society of Clinical Oncology/College of American Pathologists
CBC	Complete blood count
CCCA	Complete cell cycle arrest (Ki67≤ 2.7%)
CDK	Cyclin-dependent kinase
DL	Dose level
DLT	Dose-limiting toxicity
DNA	Deoxyribonucleic acid
ECOG	Eastern Cooperative Oncology Group
ER	Estrogen receptor
ESR1	Estrogen receptor-alpha gene
FDA	Food and Drug Administration (United States)
FSH	Follicle stimulating hormone
HCQ	Hydroxychloroquine
HER2	Human epithelial receptor-2 (HER2/neu)
JAK/STAT	Janus kinase/signal transducers and activators of transcription
Ki67	Kiel antigen, a cellular marker for proliferation
L	Letrozole
LH	Luteinizing hormonal
MBC	Metastatic breast cancer
MCF7	A hormone receptor-positive breast cancer cell line
mg	Milligrams
mTOR	Mammalian target of rapamycin
P	Palbociclib
p.o.	By mouth
PR	Progesterone receptor
PI3K	Phosphoinositide 3-kinase
PIK3CA	Phosphatidylinositol-4,5-Bisphosphate 3-Kinase Catalytic Subunit Alpha
Rb	Retinoblastoma protein
RNA	Ribonucleic acid
RP2D	Recommended phase II dose
SEER	Survey End Epidemiology Results
SMC	Safety and Monitoring Committee
T. Bili	Total bilirubin
ULN	Upper limits of normal (Institutional)
U/S	Ultrasound

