### 3.2.2 Window Component Schema and Design

## Phase II Window Component Trial Schema

- Post menopausal
- Clinical Stage I-III Breast Cancer
- ER+, HER2-negative
- No Prior Therapy

**FIGURE 2. Schema for pre-operative “window”/neoadjuvant trial.** Part 1 dose responsiveness evaluation at 400 mg/d HCQ followed by Part 2 at RP2D HCQ using same design and biopsy time points (T0 [baseline/pretreatment, T1 [after 2 weeks P+L], T2 [after addition of HCQ]), with option to proceed with surgery right after T2 biopsy or up to 24 weeks from initiation of therapy. P=continuous low dose palbociclib at 75 mg daily L=letrozole at 2.5 mg daily; HCQ=hydroxychloroquine continuous daily at assigned dose; N=number of patients; U/S=ultrasound; RP2D=recommended Phase II dose (of HCQ).

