### **3.5 Phase II Window/Neo-adjuvant Component – Dose Cohorts (Parts 1 and 2)**

To estimate the dose responsiveness of HCQ in the main outcome measures as stated on Section 2.2.3, two groups will be enrolled at the HCQ levels as shown below:

Dose Level Groups	Number of patients	Hydroxychloroquine dose	Letrozole dose	Palbociclib dose
Part 1	6	400 mg/d p.o.	2.5 mg/d p.o.	75 mg capsule p.o. daily continuously, 28-day cycle
Part 2	30	RP2D		

An initial group of 6 patients (part 1) will be enrolled at an HCQ dose of 400 mg daily sequentially, and then a second group of 30 patients (part 2) will be enrolled at the HCQ dose defined in the Phase I portion as RP2D. The main efficacy endpoint statistical plan is based on the 30 patients enrolled in part 2 as described in Section 8.0.

The dose of palbociclib for both parts 1 and 2 is fixed at a dose of 75 mg orally daily continuously without a break. Letrozole and palbociclib are given for the first 2 weeks, then after the second biopsy (T2), HCQ at the assigned dose will be added. After 4 weeks (2 weeks of HCQ) (T2), the primary endpoint will have been obtained with analysis of the surgical specimen (or research biopsy at that timepoint if additional neoadjuvant endocrine therapy or chemotherapy is indicated as standard of care. Details on dosing and dose adjustments are shown in Sections 6.1.4 and 6.2.3. Using the same population, treatment and biopsy schema, 30 patients will be enrolled for the phase II Stage 2 portion of the trial.

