### **3.6 Phase II Patient Evaluability**

Patients who meet the eligibility criteria and complete a full 4 weeks of therapy (14 days of low-dose palbociclib plus letrozole and 14 days of dose palbociclib plus letrozole with HCQ) will be considered evaluable for Phase II. In addition, the completion of biopsies at T0, T1 and T2 with interpretability of Ki67 are required for evalutability. Baseline Ki67 >5% is required to enhance the interpretability of CCCA fraction change from T1 to T2.

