## **5.3 Correlative Biomarker Studies**

### **5.3.1 Biopsies, Tissue Handling and Analysis**

All biopsies on Phase I are optional and will be done with appropriate image guidance.

Biopsies for Phase II are mandatory and will be done under ultrasound guidance by a member of the research team using standard of care imaging-guided biopsy. Local anesthesia and hemostasis protocols will be used as per standard protocol. Core needles of 18 or 16G size will be used and 3-4 core biopsies will be obtained. The first core will be placed in standard 10% formalin, and all other cores will be placed in a cryovial and snap frozen in liquid nitrogen.

All of the correlative studies (unless otherwise indicated) will be performed in the laboratory of [name] located in the Zayed building at [name]. For all the correlative analysis we will use tumor tissues collected from the biopsies and at surgical resections.

Cyclin E, and Rb immunohistochemistry (IHC) assays. FFPE tumor tissue slides will be prepared from paraffin imbedded blocks per standard methodologies and subjected to IHC analysis with 2 different antibodies: cyclin E and Rb:

Cyclin E: the anti-human C-19 polyclonal antibody (Santa Cruz Biologicals) at 1:2000 dilution will be used to stain each slide. Each slide will be scored for percent nuclear and percent cytoplasmic positive staining. Only tumor cells with greater than 5% nuclear or cytoplasmic positivity are considered as cyclin E positive. Nuclear and cytoplasmic staining scores are assigned according to the staining intensity (0 = no staining, 1 = blush staining, 2 = weak staining, 3 = intermediate staining and 4= strong staining). The nuclear and cytoplasmic scores are then combined, and four immunophenotypes are identified. First, breast tumors will be considered to be negative for cyclin E when staining is not detected in the nuclei or cytoplasm (phenotype 1). Second, in cases determined to be cyclin E+, if the nuclear staining score exceeded the cytoplasmic score, cyclin E expression is defined as predominantly nuclear (phenotype 2). Third, when the nuclear and cytoplasmic staining scores are equal,

cyclin E expression is considered to be both nuclear and cytoplasmic (phenotype 3). Fourth, if the cytoplasmic staining score is higher than the nuclear score, cyclin E expression is considered to be predominantly cytoplasmic (phenotype 4).

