### **5.3.3 Ki67 Tumor Assay and Scoring**

CLIA-approved Ki67 staining will be performed using anti-Ki67 rabbit monoclonal antibody (isotype IgG1κ, clone MIB-1, DAKO) in the diagnostic Immunohistochemistry Laboratory of Department of Pathology using an established protocol. Briefly this protocol includes de-paraffinization (30 minutes at 72°C) and rehydration with antigen retrieval performed at 100°C for 20 minutes with Tris-EDTA buffer, pH 6.0.

Endogenous peroxidase is blocked with 3% peroxide for 5 minutes. Primary anti-Ki-67 antibody (Dako, clone MIB-1) is applied at 1:100 dilution for 15 minutes. Post primary antibody detection is carried out using a commercial polymer system (Bond Polymer Refine Detection, Leica), and stain development is achieved by incubation with DAB and DAB Enhancer (Leica).

Ki67 staining will be evaluated in whole tissue sections without focusing on the hot spots. The staining will be quantitatively assessed by automated image analysis using the Aperio ScanScope AT2 scanner (Leica Biosystems, Inc., [name]). All Ki67 immunostained slides will be scanned at 20 X magnification. As Ki67 is a nuclear stain, the Genie nuclear v9.1 algorithm will be used to create a custom-made classifier. A color graphic phase of image analysis is afterward performed using red, orange, and yellow (high, medium, and low reaction, respectively) to represent positive cells, and blue to represent negative ones. A curvature threshold adjustment is made to de-cluster or

break up large groups of closely apposed nuclei when needed. The original factory algorithm is also adjusted to avoid false positives by lowering the Cytoplasmic Intensity settings. All algorithm adjustments are tested to assure accurate detection of positive and negative nuclei.

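### In Phase II patients who go to surgery, Ki67 is read on a needle core before HCQ and on the resection after it, so the T1-to-T2 change in CCCA mixes specimen type with adding HCQ

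*Combined protocol and SAP*

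**What the plan says.** **T1.** Section 5.3.1 makes Phase II biopsies mandatory and ultrasound-guided: "Core needles of 18 or 16G size will be used and 3-4 core biopsies will be obtained". The first core goes into formalin and the others are frozen. Surgery cannot supply T1 for an evaluable patient, because Section 3.6 requires a further 14 days with HCQ and a T2 reading.

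**T2.** Section 3.5 says that "the primary endpoint will have been obtained with analysis of the surgical specimen (or research biopsy at that timepoint" if more neoadjuvant treatment is indicated. Under the schedule tables in Section 5.2, superscript C says that patients who know they will have surgery at T2 "will not need a biopsy and biomarkers will be measured on the surgical specimen". Superscript D describes the T2 material as "Sample of surgical specimen (or core needle biopsy if patients is going on to standard of care neoadjuvant endocrine or chemotherapy".

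**Scoring.** Section 5.3.3 fixes one antibody, one laboratory and one automated algorithm: "Ki67 staining will be evaluated in whole tissue sections without focusing on the hot spots". It gives no minimum number of nuclei and does not mention core versus resection.

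**Endpoint and test.** Section 2.2.3 defines the primary endpoint as the increase in the percentage with CCCA (Ki67 at or below 2.7%) from T1 to T2. Section 8 tests the T2 count with a two-stage Simon design and contains no analysis by specimen type.

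**Conflicting wording.** The Figure 2 legend (Section 3.2.2) describes T2 "with option to proceed with surgery right after T2 biopsy or up to 24 weeks from initiation of therapy". Section 3.6 says "the completion of biopsies at T0, T1 and T2 with interpretability of Ki67 are required" for evaluability. Superscript C first places a third biopsy at week 5 for patients going to surgery, then waives it. The stage 1 rule in Section 8 counts CCCA by tumor biopsy.

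**The concern.** For a patient who has surgery at day 29, the specimen changes from core to resection at exactly the step where HCQ is added. CCCA is a hard cut-off, so any systematic difference in Ki67 between the two specimen types moves patients across 2.7% whether or not HCQ does anything. The trial has one arm, so no concurrent control would absorb such a shift.

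The mix at T2 is neither random nor fixed in advance. Sections 1.3 and 5.2.3.2 leave the choice between surgery and further neoadjuvant treatment to clinical judgment and patient preference. Patients with a core at both times are not affected.

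**Working it through.** **1. The plan's own figures.** Inputs from Section 8: stop if 6 or fewer of 11 show CCCA; declare promising if at least 17 of 25 do; rates 50% and 75%. With b the binomial probability,

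P(promising | p) = sum over x = 7 to 11 of b(x; 11, p) × P(Bin(14, p) ≥ 17 − x).

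- At p = 0.50: 4.58% (stated alpha 4%).
- At p = 0.75: 80.05% (stated power 81%).
- P(Bin(11, 0.50) ≤ 6) = 0.7256 (stated 0.73).

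The design reproduces, apart from small differences in alpha and power. The comparisons below use 4.6% and 80%.

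**2. Inputs that the documents do not give (assumptions).**
- s, the SD of ln Ki67 at T2: 1.0 to 1.3.
- R, the ratio of a resection reading to a core reading of the same tumor: 0.80 to 1.25.
- f, the share of T2 readings made on resections: 25% to 100%.

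**3. Model.** If p is the CCCA rate on cores and ln Ki67 is normal, the rate on resections is

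p_R = Φ(Φ⁻¹(p) − ln R / s),

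and the rate seen at T2 is p_eff = (1 − f)p + f·p_R. This p_eff goes into the formula in step 1.

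**4. Numbers put in, at the ends of the range.**
- HCQ adds nothing, R = 0.95, s = 1.3, f = 0.25: p_R = Φ(0.0513/1.3) = 0.5157; p_eff = 0.75 × 0.50 + 0.25 × 0.5157 = 0.5039; P(promising) = 5.0%.
- HCQ adds nothing, R = 0.80, s = 1.0, f = 1: p_R = Φ(0.2231) = 0.5883; P(promising) = 20.5%.
- True rate 75%, R = 1.05, s = 1.3, f = 0.25: p_R = Φ(0.6745 − 0.0488/1.3) = 0.7379; p_eff = 0.75 × 0.75 + 0.25 × 0.7379 = 0.7470; power 79.1%.
- True rate 75%, R = 1.25, s = 1.0, f = 1: p_R = Φ(0.6745 − 0.2231) = 0.6741; power 51.5%.

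**5. Results.** Each cell runs from s = 1.3 with f = 25% to s = 1.0 with f = 100%.

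| Resection reading relative to core | Quantity | Result | With no shift |
|---|---|---|---|
| 5% lower | false positive rate | 5.0 to 6.9% | 4.6% |
| 10% lower | false positive rate | 5.4 to 10.1% | 4.6% |
| 20% lower | false positive rate | 6.4 to 20.5% | 4.6% |
| 5% higher | power | 79.1 to 74.9% | 80% |
| 10% higher | power | 78.2 to 69.3% | 80% |
| 25% higher | power | 75.4 to 51.5% | 80% |

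**6. What the table depends on.** The Simon rule never uses a patient's T1 value. It compares the T2 count with a fixed 50%, which Sections 2.2.3 and 8 describe as the rate on low-dose palbociclib plus letrozole (T1). The table applies if that 50% is taken to be a rate on core readings. The T1-to-T2 change in Section 2.2.3 needs no such assumption: it is affected directly in every patient whose T2 is a resection.

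**The case against.** The best defense is that most of the measurement is already common to both specimens. Antibody, laboratory, algorithm and the avoidance of hot spots are the same, Section 5.3.1 names tissue from biopsies and from resections as the material, and superscript D refers the surgical sample to Section 5.3. That stands, and it narrows the gap to three things: no fixation instruction for the surgical sample, no common minimum nuclei count, and no analysis by specimen type.

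It is also fair that size, direction, SD and surgical share are all assumed. With a difference of about 5% and a quarter of readings surgical, the effect is negligible. The range therefore has to include that region.

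Three stronger readings are tempting and not supported:
- A reader might infer that the Simon decision is necessarily biased. The documents do not say that the 50% is a core-based figure; Section 2.2.3 calls it a reference probability.
- A reader might infer that resections are handled differently before fixation and scored over a far larger area. The documents state neither: superscript D speaks of a sample and gives no size.
- A reader might infer that counting more nuclei on a resection is itself a large bias. Counting error moves tumors across 2.7% in both directions and largely cancels over a population, so results for a tumor just above the cut-off do not measure the net effect.

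**Conclusion.** The concern holds in a limited form. If the plan is followed as written, the specimen type changes at T2 for the surgery subset, and nothing in Section 5.3.3 or Section 8 controls or examines that. In those patients the change in CCCA cannot be attributed to HCQ alone. The formal test is affected only to the extent that its 50% benchmark represents core readings.

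The magnitude is hypothetical. Under the assumptions above, the false positive rate lies between 5.0% and 20.5% and power between about 79% and 52%, depending on the direction of the difference. The documents do not show that a core-resection difference exists, and a reader should not take the upper ends as expected values. This is an inexpensive improvement that should be made, not a flaw that invalidates the design.

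**What to change.** 1. Reconcile the T2 specimen wording in the Figure 2 legend (3.2.2), Section 3.6, superscripts C and D (5.2) and the stage 1 rule in Section 8, so that all state what material is read at T2.
2. State that the superscript D sample is taken as cores of the same gauge from the fresh surgical specimen, placed in formalin at once, and processed and scored as at T1.
3. Set one minimum nuclei count for T1 and T2, chosen by the pathology laboratory. Say whether samples below it are flagged or count as not interpretable under Section 3.6, since the latter would lead to replacement under Section 3.7.
4. Prespecify as a sensitivity analysis T2 CCCA and the T1-to-T2 change by specimen type, including core-core pairs only.

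Item 4 cannot replace item 2. The surgery and non-surgery groups also differ clinically, and the groups are small. With an assumed 12 and 13 of 25 patients, the standard error of a difference in CCCA rates near 50% is √(0.25 × (1/12 + 1/13)) = 0.20, or 20 points, against a shift of at most about 9 points in step 4 of the working when HCQ adds nothing (0.5883 − 0.50). Item 2 in turn does not remove effects that arise during the operation before excision, which is why both are wanted.

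The cost is a little specimen handling and one extra descriptive table. No procedure is added for the patient, and treatment and sample size do not change. Matched handling has to be set prospectively, because it cannot be restored once the tissue is fixed.

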### 5.2.1 Baseline Assessments

All patients will undergo a baseline standard evaluation for newly diagnosed breast cancer including (note that some baseline tests can be done prior to day 1 (week 1) as shown on Tables 1 and 2):

- Review of systems all organ systems will be examined.
- Physical examination, vital signs, weight, height, and evaluation of ECOG performance status.
- Standard of care pathological diagnosis of breast cancer, imaging (Phase II: breast ultrasound; Phase II: CT, MRI) and clinical staging.
- Laboratory studies: CBC/differential, electrolytes, BUN, creatinine, glucose, albumin, AST, ALT, Total Bilirubin, Alkaline phosphatase, PT, PTT.
- Urinalysis
- Ophthalmological exam per latest guidelines of the American Academy of Ophthalmology (AAO) for baseline screening with HCQ treatment.
- Fresh Tumor Biopsy (Phase II only).
- Research blood draw (Phase II only).
- Baseline urine or serum pregnancy test for both Phase I and II.

ECOG performance status
Grade ECOG status
0 - Fully active, able to carry on all pre-disease performance without restriction.
1 - Restricted in physically strenuous activity but ambulatory and able to carry out work of a light or sedentary nature e.g., light housework, office work.
2 - Ambulatory and capable of all self-care but unable to carry out any work activities. Up and about more than 50% of waking hours.
3 - Capable of only limited self-care, confined to bed or chair more than 50% of waking hours.
4 - Completely disabled. Cannot carry on any self-care. Totally confined to bed or chair.
5 - Dead

### 5.2.2 Evaluation During Study Phase II

Patients will be evaluated with an organ-specific review of systems and physical exam at weeks 2, 3, 4, and those who choose and are eligible to go beyond the “window period” (as described in Sections 1.3, 3.2.2 and 5.2-Table 2) and stay on study until definitive surgery at week 16 to 24 will undergo additional evaluation at weeks 6, 8 and every 4 weeks thereafter until the last pre-operative visit between week 16 and 24 at the discretion of the medical and surgical oncologist as shown on Table 2.

### 5.2.3 Treatment Duration

#### 5.2.3.1 Phase I

Patients will receive treatment for at least until week 8 as long as there are no DLTs in the first 4 weeks, or significant toxicities requiring treatment discontinuation in the judgment of the treating investigator, and no evidence of clinical progression. At week 8, if tumor assessment by scans show evidence or response by RECIST 1.1 criteria (applies only to patients with

measurable disease), they will be allowed to stay on treatment as long as there is no evidence of progression or significant toxicities up to a maximum of 1 year. This maximum timeframe is due to concerns about HCQ toxicity, which could be duration-dependent. Patients who show progression or stability of disease at week 8 will come off study and can continue standard treatment (standard dose palbociclib and letrozole) or alternate therapy at the discretion of the treating physician.

